The DSMB meets at least annually throughout the trial once the protocol has been approved. In addition to the DSMB members, meetings are attended by representatives from the Coordinating Center, the Steering Committee (including the study chair, vice chair, and others as deemed appropriate), and the NHLBI. Only the DSMB members may vote.

19. Human Subjects

Description of Consent Process

To participate in DASH2, participants must provide written, informed consent using procedures reviewed and approved by each clinical center's local IRB. In particular, even though consent to participate in DASH2 must be obtained for all stages of the study, the process and timing of consent may vary by clinic. Descriptions of each clinical center's consent procedures are included as part of the Manual of Procedures, and copies of each clinical center's consent documents are kept at the Coordinating Center. The consent forms must include all procedures done as part of screening, run-in, and feeding.

Elements of Consent

Consent to participate in a research study includes the eight elements listed below. An appropriate consent process must include all elements.

- 1. Participants must be advised that the study involves research. Staff must explain the purposes of the research, the expected duration of participation, and a description of the procedures to be followed, including identification of experimental procedures.
- 2. Anticipated benefits of the trial must be explained to the participant.
- 3. Attendant discomforts and risks "reasonably to be expected" must be described.
- 4. Appropriate alternative procedures that might be advantageous for the participant must be disclosed.
- 5. The extent, if any, to which confidentiality of records identifying the participant will be maintained must be described.

- 6. Prospective participants must be advised of the availability or non-availability of medical treatment or compensation for physical injuries incurred as a result of participation in the study, and, if available, what they consist of, or where further information can be obtained.
- 7. Persons responsible for the study must explain whom a participant can contact for answer to pertinent questions about the research and his or her rights, and whom to contact in the event of a research-related injury.
- 8. Participants must be told that participation is voluntary, refusal to participate will involve no penalty or loss of benefits to which the participant is otherwise entitled, and the participant may discontinue participation at any time without penalty or loss of benefits to which he or she is otherwise entitled.

Confidentiality

Participants in the DASH2 study are protected by the customary constraints on confidentiality of participant data. Wherever feasible, study forms identify participants only by an anonymous study ID number. Forms and electronic data are protected by reasonable security procedures including locked rooms and/or file cabinets for paper documents and coded security access for electronic data. Access to identifying information will be limited to study personnel with a need for such access. Personnel involved in DASH2 must agree not to disclose any information that might be protected by confidentiality policies to persons who do not work for the study or who do not have a need to know the information. No published data will include information that would permit readers to identify any individual participant in the study. When the study database is made available to clinical centers and to the Program Office, it will not include actual identities and contact information for participants. Such information is retained only under lock and key at the individual clinical centers and at the Coordinating Center for use in the event the future follow-up of the study participants is necessary.

Data Integrity

Data maintained at the clinical centers are internally backed up each day onto a second hard drive located in the PC. Copies of the master database maintained at the Coordinating Center are backed up daily and archived off-line on a daily, weekly, monthly, and yearly basis.

Risks

The DASH2 study should not involve any major health risk to participants. The most likely physical health risks associated with participation are gastrointestinal upset (e.g., bloating), increased frequency and bulk of stools (resulting from the high fiber content of some diets), and minor discomfort from the venipunctures. These effects are either transient or readily reversible once off the study diets. The DASH experience suggests that GI discomfort, though common, is generally minor and appears to subside over time. Participants are monitored for reactions to the diets and, if necessary, the diet can be terminated (although this was not necessary during the DASH study).

Depending on a participant's baseline diet, some of the dietary patterns and sodium levels under study may lead to slight, transient increases in blood pressure that are not sufficient to significantly raise risk for any morbid consequences. Participant blood pressure is monitored weekly during the feeding periods and potentially "at-risk" individuals, including those taking blood pressure medications, are excluded during screening. In addition, participants are referred for medical evaluation if their blood pressure exceeds pre-established "escape" levels, and are dropped from the study if they subsequently need to start on blood pressure medication. Additional risks to study participants include: accidental breach of confidentiality; the inconvenience of having to come to the clinic each day to eat a meal and only being allowed to eat assigned study foods; the inconvenience of collecting 24-hour urine specimens; and the inconvenience of wearing an ABPM device.

Benefits

The benefits associated with participation in the study include: free food for 15 weeks, regular blood pressure monitoring, cash reimbursement (amounts vary by center), and free laboratory tests that have a small possibility for early diagnosis of an illness. Participants will also have the satisfaction of participating in a clinical trial with potentially major public health implications.

We anticipate that a majority of participants randomized to the combination dietary pattern will experience a reduction in blood pressure while on this diet. In addition, all participants will receive two months of food that is at or below current US recommendations for sodium intake. Changes in blood pressure associated with the DASH2 diets, however, whether up or down, are unlikely to be of any clinical significance over the relatively short duration of the study.

Gender and Minorities

The DASH2 study will recruit a sample that is 50% African American and 50% female. Recruitment of minorities and women is formally monitored quarterly and reports forwarded by NHLBI. Minorities other than Blacks will also be included, although no targets are set for this category and they will be grouped with White participants for analysis. All of the participating centers have demonstrated in DASH their ability to recruit large numbers of African Americans and women. Further, we have specifically powered the study to have good power to detect sodium effects for race and gender subgroups.

20. References

- 4. The Joint National Committee on Detection, Evaluation and Treatment of High Blood Pressure. The fifth report of the Joint National Committee on Detection, Evaluation and Treatment of High Blood Pressure. Arch Intern Med 1993; 153:154-183.
- 6. Working Group on Primary Prevention of Hypertension, National High Blood Pressure Education Program. Working Group Report on Primary Prevention of Hypertension. Arch Intern Med 1993; 153:186-208.

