Rationale: Much of the research on the relationship between sodium intake and blood pressure occurs in the upper ranges (i.e., > 50 mmol) of intake. Although some evidence exists for a greater than expected lowering of blood pressure at very low levels of sodium intake, an analysis of INTERSALT data reported that no model fit the data better than a linear model. This specific aim will help fill this knowledge gap.

We hypothesize that the relationship between sodium and blood pressure is not linear, with greater than linear responsiveness at lower levels of sodium. We will test the above four specific aims using RZ-SBP as the primary outcome variable and RZ-DBP and 24-hour SBP as secondary outcome variables.

Other Objectives

We also address the following additional objectives.

- 1. To assess whether the observed effects of both the DASH combination dietary pattern and sodium intake on blood pressure vary according to baseline characteristics such as race, sex, baseline blood pressure, body mass index, waist circumference, education, and diet prior to entry into the study.
- To determine the extent to which age influences blood pressure response to the DASH combination diet and to sodium reduction. Because salt sensitivity increases with age, we would expect age to be an effect modifier for the sodium intervention. Although age had no apparent effect on response to the DASH combination diet, an effect may be present when both the DASH combination diet and sodium reduction are combined.
- 3. To determine the extent to which renin profile influences blood pressure response to the DASH combination diet and sodium reduction.
- 4. To assess the effects of the DASH combination dietary pattern and sodium intake (*Specific Aims 1-4*, above) on selected measures of ambulatory blood pressure, including 24-hour DBP, waking SBP and DBP, and sleeping SBP and DBP. In addition, as exploratory analyses, we will assess these ambulatory pressure indices in the analyses outlined in *Other Objectives* 1-3, above.
- 5. To assess the effect of the DASH combination dietary pattern and sodium intake on dipper/nondipper status (a measure of nocturnal blood pressure decline).

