Unlike DASH, where the primary outcome was diastolic blood pressure and systolic blood pressure was secondary, the primary outcome in DASH2 is systolic blood pressure, with diastolic and 24-hour SBP secondary. Although systolic and diastolic blood pressure are highly correlated with each other, systolic blood pressure was chosen as the primary outcome because large epidemiologic studies have found that systolic blood pressure is a better predictor than diastolic for cardiovascular disease (70,71).

Rationale for Other Objectives

Baseline Characteristics

Because of evidence that the blood pressure response to sodium intake is greater in African Americans than in non-African Americans (21-25) and greater in women than in men (19,26,27), we designed DASH2 to test Specific Aim #1 separately by race and sex. Because of the public health importance of the potential for risk reduction in nonhypertensives as well as hypertensives, the blood pressure response to reduction in sodium intake will be studied separately in the hypertensives and non-hypertensive participants in DASH2. Secondary analyses of this and the other specific aims for subgroups defined by sex, race, baseline blood

pressure, age, education, body mass index, waist circumference, and diet prior to entry into the study will enhance the generalizability of the results. For example, DASH found that the blood pressure lowering effects of the combination diet were present in a broad array of subgroups and were significantly greater in hypertensive participants than in non-hypertensive participants (7). The effect of age on blood pressure response to diet will be examined as it has been reported that older people have greater blood pressure responsiveness to salt intake than younger people (13a). Waist circumference is used as an indicator of central adiposity (72,73). Growing evidence indicates that centrally located adiposity is associated with carbohydrate metabolism abnormalities, hyperlipidemia, and hypertension (74,75). In DASH2, we expect centrally located fat to be associated with higher blood pressure for any given level of body fat, and increased central fat may enhance the blood pressure lowering effects of the intervention diets (75).

Ambulatory Blood Pressure Monitoring (ABPM)

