Hypertensive individuals display a broader range of plasma renin levels than do nonhypertensive individuals (77). Laragh (78) found that hypertensives with low renin levels (about 20% of essential hypertensives) responded especially well to "volume" treatment, i.e., diuretics, while those with high renin levels responded to beta-blockers, which reduce renin levels. These findings formed the basis for the volume-vasoconstrictor theory of hypertension pathophysiology (78). Of particular relevance to DASH2, low renin levels are reportedly more

common in African Americans and older persons, also populations with greater salt sensitivity. Thus, the renin status of DASH2 participants may be a confounder for the blood pressure response to salt intake. In addition, Resnick et al. (79) reported that low renin individuals have a greater antihypertensive response to calcium supplementation, suggesting that the response to the DASH combination diet itself may be affected by renin status. Based on these considerations, we will categorize renin status in DASH2 by measuring plasma renin activity at the end of the 50 mmol sodium diet period. We have chosen this level of sodium because renin levels will be maximally stimulated, providing the clearest definition of low renin participants (80,81).

Biological Storage Samples

Numerous endogenous vasoactive substances and candidate genes related to blood pressure or cardiovascular risk may influence blood pressure response to the DASH combination diet and to sodium reduction. To facilitate future investigation of biological variables (e.g., plasma renin and angiotensin) and candidate genes (e.g., angiotensinogen), we will store plasma, serum, and 24-hour urine specimens taken at baseline (screening) and at the end of each feeding period, and buffy coat specimens taken once during intervention.

4. Study Design

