For all four aims, further secondary analyses will adjust for the potentially confounding effects of race, sex, age, body mass index, education, physical activity, and alcohol intake. Interaction terms are used to determine if any observed treatment effects differ for various subgroups. Additional analyses will test whether baseline renin status influences treatment differences.

Handling of missing data.

Participants not completing the post-randomization follow-up (either due to nonattendance at data collection visits or to protocol escape levels) are likely to represent a nonrandom subset of the overall randomized population. For example, those individuals who are required to initiate antihypertensive medications are likely to be the participants who would have had the highest end-of-intervention blood pressure levels. End-of-intervention blood pressure values for such participants are discussed in section 12 (Outcomes Measures).

Because of the cross-over nature of the study design, some dropouts will not have any BP measurements for one or more sodium levels. As described in section 12, we use the average of these individuals' screening blood pressures as their end-of-intervention blood pressures. The rationale for this rule is that, in essence, these individuals are just very noncompliant with the study diets, and our best estimate of their blood pressure on their usual diets is the average of their screening blood pressures. The only exception to this rule is for those individuals who are randomized but who never start any of the intervention feeding periods. Since loss to follow-up in these individuals cannot be related to treatment assignment, they are treated as if they were never randomized and excluded from all analyses.

Finally, subject to the preceding considerations, analyses are conducted using an intention-totreat philosophy, whereby each randomized participant is included in each analysis according to his/her randomly assigned diet group.

15. Sample Size / Statistical Power

The proposed sample size of 400 participants (200 in each of the combination and control diet arms) was selected to provide adequate power, both overall and within subgroups, for addressing specific aims #1 and #2. This section summarizes power computations to address all four of its specific aims. We assume two-sided alternative hypotheses for each specific aim, and we also include allowance for multiple testing adjustment, as indicated above.

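### Effect modification by age, baseline blood pressure, BMI, waist, prior diet and renin is worded as group comparison; a continuous interaction term should be the main test, because any grouping loses information

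*Protocol*

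**What the plan says.** The objectives are neutral about method. Other Objective 2 (section 2) is "To determine the extent to which age influences blood pressure response to the DASH combination diet and to sodium reduction". Objective 3 asks the same of renin profile, and Objective 1 asks whether effects vary with race, sex, baseline blood pressure, BMI, waist, education and prior diet.

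The method wording points to groups:

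- Section 3, Baseline Characteristics: "Secondary analyses of this and the other specific aims for subgroups defined by sex, race, baseline blood", continuing "pressure, age, education, body mass index, waist circumference, and diet prior to entry into the study will enhance the generalizability of the results".
- Section 3, Plasma Renin: "we will categorize renin status in DASH2 by measuring plasma renin activity at the end of the 50 mmol sodium diet period", so as to define low-renin participants clearly.
- Section 14, after Aim #4: "Interaction terms are used to determine if any observed treatment effects differ for various subgroups". The next sentence there tests renin status, not renin level.

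The Protocol gives no number of groups and no cut-point for age, BMI, waist, prior diet or renin. Its only split of blood pressure with a stated proportion is hypertensive status, about 30/70 (section 6, Study Sample). Its only low-renin share is a background figure: "hypertensives with low renin levels (about 20% of essential hypertensives".

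**The concern.** Age, blood pressure, BMI, waist circumference, nutrient intake and plasma renin activity are all measured on continuous scales. A comparison of groups shows whether the groups differ, and the answer depends on where the cut falls. It does not estimate how response changes per year of age or per unit of log renin, which is what asking about extent calls for. Cutting a continuous modifier also lowers the power of the interaction test.

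The Protocol holds prior expectations here. It expects age to modify the sodium effect, thinks central fat may enhance the diet effects, and suggests that renin status may affect response. A modifier missed because it was grouped would leave one of these stated questions wrongly answered.

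**Working it through.** **Inputs.** From section 15: 400 participants, 200 per diet; SBP variance components 150 between and 40 within; two-sided 0.05. Section 12 averages five daily readings, so the error variance of an end-of-period mean is 40/5 = 8. Assumed, because the Protocol gives no distribution or form: a normal modifier with linear modification. Alternatives are shown in step 5.

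**1. The Protocol's own figure.** For a sodium contrast within one diet, SE = √(2 × 8/200) = 0.283. With two Holm tests the critical value is 2.241. The detectable effect at 90% power is (2.241 + 1.282) × 0.283 = 1.00 mm Hg. At 80% and 70% power it is 0.87 and 0.78. The Protocol states 1.0, 0.9 and 0.8, so the variance inputs are understood correctly. It gives no power for effect modification by a covariate.

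**2. Information kept by grouping.** The share kept on a linear interaction is the between-group variance of the modifier divided by its total variance. For two groups cut at proportion p of a normal variable this is φ(z_p)² / [p(1 − p)].

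- Median split: 0.3989²/0.25 = 0.637
- 20/80 split: 0.2800²/0.16 = 0.490

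For three or more equal groups the same ratio was computed numerically.

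| Grouping | Kept | Lost | Equivalent of 400 |
|---|---|---|---|
| Median split | 0.637 | 36% | 255 |
| 20/80 (illustrative) | 0.490 | 51% | 196 |
| Tertiles | 0.793 | 21% | 317 |
| Quartiles | 0.861 | 14% | 344 |
| Quintiles | 0.897 | 10% | 359 |

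**3. Power.** Take an interaction with 80% power as measured, so that its expected z is 1.96 + 0.84 = 2.80. After grouping, power = Φ(2.80 × √kept − 1.96).

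- Median split: 2.80 × 0.798 − 1.96 = 0.27, power 61%
- Tertiles: 2.80 × 0.891 − 1.96 = 0.53, power 70%
- Quartiles: power 74%
- 20/80: 2.80 × 0.700 − 1.96 = 0.00, power 50%

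With three or more groups this assumes a one-degree-of-freedom trend over the group means. A general test of heterogeneity would do less well against a linear effect.

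**4. On the mm Hg scale.** For the sodium effect within one diet (n = 200, unadjusted 0.05), the slope per SD of the modifier detectable at 80% power is 2.80 × 0.283 = 0.79 mm Hg. It rises to 0.79/√0.637 = 0.99 after a median split and 0.79/√0.490 = 1.13 after a 20/80 split.

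**5. Other shapes.** A uniform modifier loses 25% at a median split and 11% with tertiles. A right-skewed modifier (lognormal, σ = 0.5) that acts linearly on its raw scale loses 48% at a median split, 32% with tertiles and 73% if only the lowest 20% is cut off. Some loss occurs under every grouping examined; its size depends on the cuts and on the shape.

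**The case against.** The strongest case against is that the Protocol leaves this open. The objectives are neutral, section 3 also says without grouping that the effect of age will be examined, section 12 says that renin level is measured, and an interaction term can hold a continuous covariate. The subgroup sentence is background rationale, aimed at generalisability, and its list includes sex, race and education. The choice between continuous and grouped could be left to an analysis plan. All of this stands against reading the Protocol as ruling out a continuous analysis. It does not remove the point: wherever a method is worded, it is by subgroup or category, and an analysis plan that followed it would group.

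Second, a reader might infer that a third to a half of the information will be lost. The documents do not support that as a fact. It needs exactly two groups, a normal modifier and linear modification, and no number of groups is fixed. The 20% share describes essential hypertensives in cited work and is not a planned cut here. The 30/70 split belongs to the formal hypertension analysis, which is not questioned.

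Third, the absolute effects are small. With both diets pooled, a median split detects a difference in sodium effect of about 2.80 × √(16/200 + 16/200) = 1.1 mm Hg between halves, while section 15 uses 3 mm Hg as its public health reference. That limits the stakes, although 3 mm Hg refers to a population-wide reduction, not to a difference between subgroups. Nor are interactions shown to be the weakest tests: at 90% power section 15 lists 1.4 mm Hg for Aim #3, against 1.5 for Aim #2 and 1.7 for Aim #4.

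Fourth, low renin is a clinical class, and response could have a threshold. A linear term in log renin is then the wrong shape, so the continuous analysis is not free of risk. This stands and is the reason to keep the category as well.

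**Conclusion.** The point holds as a low-cost improvement to secondary and exploratory analyses. The method wording is by group, the question asked about age and renin is one of extent, and no commitment to a continuous term bridges the two. For a normal modifier with linear modification, the loss runs from about 10% (quintiles) through 21% (tertiles) to 36% (median split), and to about 51% at an illustrative 20/80 split. An interaction with 80% power as measured falls to about 61% at a median split and 70% with tertiles. These figures are conditional on the assumed distribution, form and number of groups. The primary analysis, the sample size and the formal race, sex and hypertension analyses are unaffected. The timing of the renin sample is a separate question.

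**What to change.** In section 14, state that modification by age, baseline blood pressure, BMI, waist circumference, prior nutrient intake and log renin is tested mainly by sodium-by-covariate and diet-by-covariate terms with the covariate continuous, plus one curvature check for each. Keep subgroup estimates and the low-renin category as supportive display, and adjust the wording in section 3 to match. Leave the formal analyses by race, sex and hypertensive status as they are.

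The cost is a few sentences: the data and the mixed model are the same. The small downside is the assumed linear form, which the curvature check and the retained low-renin category address.
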